### **4.3 Exclusion Criteria**

1. Documented active systemic light chain amyloidosis.
2. Active plasma cell leukemia.
3. Eastern Cooperative Oncology Group (ECOG) Performance Status greater than 2.
4. Persistent non-hematological toxicity (except for peripheral neuropathy) from a prior treatment which has not resolved to at least Grade 2 or better by Cycle 1 Day 1 (C1D1).
5. Severe hepatic dysfunction with either:
  - a. Total bilirubin  $> 1.5 \times$  ULN ( $> 3x$  ULN in subjects with Gilbert's syndrome [hereditary indirect hyperbilirubinemia]), and/or
  - b. AST and/or ALT  $> 2.5 \times$  ULN
6. Severe renal dysfunction with an estimated creatinine clearance (CrCl) of  $< 15$  mL/min calculated using the Cockcroft and Gault formula.
7. Impaired hematopoietic function with either:
  - a. White blood cell count  $< 1,500/\text{mm}^3$ , and/or

- b. Absolute neutrophil count < 1000/mm^3, and/or
- c. Hemoglobin < 8.0 g/dL, and/or
- d. Platelet count < 100,000/mm^3 (for patients in whom ≥ 50% of bone marrow nucleated cells are plasma cells, platelets ≥ 75,000/mm^3 are acceptable).

8. Blood (or blood product) transfusions or blood growth factors within 7 days of C1D1.
  - a. Use of hematopoietic growth factor support is acceptable, including erythropoietin (EPO), darbepoetin, granulocyte-colony stimulating factor (G-CSF), granulocyte macrophage colony stimulating factor (GM-CSF), and platelet stimulators (e.g., eltrombopag or romiplostim). However, patients must be platelet transfusion independent for > 1 week in order to be enrolled in the study.
9. Radiation, chemotherapy or immunotherapy, or any other anticancer therapy within 2 weeks prior to C1D1, or radio-immunotherapy within 6 weeks prior to C1D1. Patients on long-term glucocorticoids during Screening do not require a washout period. Prior radiation is permitted for treatment of fractures or to prevent fractures, as well as for pain management.
10. Patients with history of spinal cord compression with residual paraplegia.
11. Treatment with an investigational anti-cancer therapy within 3 weeks prior to C1D1.
12. Prior autologous stem cell transplantation < 1 month, or allogeneic stem cell transplantation < 3 months prior to C1D1.
13. Active graft versus host disease after allogeneic stem cell transplantation.
14. Life expectancy < 3 months.
15. Major surgery within 4 weeks prior to C1D1.
16. Active, unstable cardiovascular function with either:
  - a. Symptomatic ischemia
  - b. Uncontrolled clinically significant conduction abnormalities (e.g., patients with ventricular tachycardia on antiarrhythmics are excluded; patients with 1st degree atrioventricular (AV) block or asymptomatic left anterior fascicular block/right bundle branch block (LAFB/RBBB) will not be excluded)
  - c. Congestive heart failure (CHF) of New York Heart Association (NYHA) Class ≥ 3
  - d. Myocardial infarction (MI) within 6 months prior to C1D1
  - e. Screening 12-lead ECG showing a baseline QT interval as corrected by Bazett's formula (QTc) > 470 msec
17. Uncontrolled active hypertension
18. Venous thromboembolism within 6 months prior to C1D1 or a known inherited thrombophilia
19. Inability to receive either prophylactic or therapeutic anticoagulation as determined appropriate by the Investigator
20. Uncontrolled active infection requiring parenteral antibiotics, antivirals, or antifungals within one week prior to C1D1
21. Any active gastrointestinal dysfunction that prevents the patient from swallowing tablets or interferes with absorption of study treatment
22. Currently pregnant or breastfeeding. Lactating females must agree not to breast feed while receiving selinexor, pomalidomide and/or clarithromycin
23. A serious psychiatric or medical condition which, in the opinion of the Investigator, could interfere with treatment
24. Hypersensitivity or contraindication to selinexor, pomalidomide, dexamethasone and/or clarithromycin
25. Prior exposure to a SINE compound, including selinexor
26. Concomitant use of any strong CYP3A4 and/or CYP1A2 inhibitors (see Appendix 1) or other restricted drugs (see section 7.8.11)

27. Unable to obtain commercial clarithromycin, pomalidomide and dexamethasone through a regular and/or specialty pharmacy.
28. Unable or unwilling to register into the mandatory POMALYST REMS™ program and comply with its requirements.
29. Male and female patients unwilling or unable to use effective methods of contraception throughout the study and for three months following the last dose. Acceptable methods of contraception are condoms with contraceptive foam, oral, implantable or injectable contraceptives, contraceptive patch, intrauterine device, diaphragm with spermicidal gel, or a sexual partner who is surgically sterilized or post-menopausal.
  - a. Female patients of childbearing potential must agree to use dual methods of contraception and have a negative serum pregnancy test at Screening.
  - b. Male patients must use an effective barrier method of contraception if sexually active with a female of child-bearing potential.

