### **6.1.1 Screening Visit (-21 to -1 days before start of treatment)**

- Informed consent
- Inclusion and exclusion criteria
- Demographics
- Medical history
- Adverse events
- Concomitant medications
- QOL assessment
- Height
- Weight
- Vital signs
- Complete physical exam
- 12-lead ECG (may be performed on C1D1)
- ECOG PS (may be performed on C1D1)
- CBC with differential
- TSH (may be performed on C1D1)
- Complete serum chemistry
- Pregnancy test
- SPEP and serum immunofixation
- UPEP (24-hr urine) and urine immunofixation
- Quantitative Ig levels
- Serum FLC
- LDH and  $\beta$ 2-microglobulin
- Skeletal survey
- Plasmacytoma assessment
- Bone marrow biopsy and aspirate

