### **6.1.2 Treatment Phase**

#### **6.1.2.1 Visit 1 (baseline; Cycle 1 Day 1)**

- Medication dispensation
- Adverse events
- Concomitant medications
- Dose intensity
- QOL assessment
- Weight
- Vital signs
- Symptom-directed physical exam
- 12-lead ECG (may be performed on Screening visit)
- ECOG PS (may be performed on Screening visit)
- CBC with differential
- TSH (may be performed on Screening visit)
- Complete serum chemistry
- Pregnancy test

- SPEP and serum immunofixation
- UPEP (24-hr urine) and urine immunofixation
- Quantitative Ig levels
- Serum FLC
- Skeletal survey
- Plasmacytoma assessment

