#### **7.8.14 Instructions for initiation of a subsequent cycle**

A new course of treatment may begin on the scheduled day 1 of a new cycle if:

- Absolute neutrophil count (ANC)  $\geq$  1,000 cells/mm^3
- Platelets count  $\geq$  75,000/mm^3
- Any drug-related somnolence, rash, peripheral neuropathy, sinus bradycardia/other cardiac arrhythmia, allergic reaction/hypersensitivity, dyspepsia, gastritis, gastric or duodenal ulcer or confusion or mood alterations that may have occurred has resolved to  $\leq$  grade 1 severity.
- Any other drug-related non-hematologic adverse events that may have occurred have resolved to  $\leq$  grade 2 severity.

If these conditions are not met on Day 1 of a new cycle, the subject will be evaluated weekly and a new cycle of treatment will not be initiated until the toxicity has resolved as described above.

If the toxicity does not resolve within four weeks, the patient will be taken off the study. If the dosing of selinexor, clarithromycin, pomalidomide or dexamethasone was halted during the previous cycle and was restarted with a one-level dose reduction without

requiring an interruption for the remainder of the cycle, then that reduced dose level will be initiated on day 1 of the new cycle.

If the dosing of selinexor, clarithromycin, pomalidomide or dexamethasone was omitted for the remainder of the previous cycle or if the new cycle is delayed due to toxicity newly encountered on the scheduled day 1, then the new cycle will be started with dose modifications as described in Tables 3 and 4.

If the start of a new cycle is delayed more than 4 weeks, the patient will be taken off study.

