### **8.2 Participant Discontinuation/Withdrawal from the Study**

Participants are free to withdraw from participation in the study at any time upon request. Patients who elect to discontinue study treatment should be encouraged to continue in

the study so that follow-up information on disease progression and survival status may be obtained. However, patients may elect to withdraw consent and decline further participation in the trial. All patients will be followed until disease progression, withdrawal of consent, death or loss to follow up.

An investigator may discontinue or withdraw a participant from the study for the following reasons:

- Pregnancy
- Significant study intervention non-compliance
- If any clinical adverse event (AE), laboratory abnormality, or other medical condition or situation occurs such that continued participation in the study would not be in the best interest of the participant
- Disease progression
- If the participant meets an exclusion criterion (either newly developed or not previously recognized) that precludes further study participation
- Participant lost to follow-up after three attempts to contact subject to schedule study visit.

The reason for participant discontinuation or withdrawal from the study will be recorded on the eCRF. Subjects who sign the informed consent form but do not receive the study intervention may be replaced. Subjects who sign the informed consent form, and receive the study intervention, and subsequently withdraw, or are withdrawn or discontinued from the study, will not be replaced.

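### The 7-day transfusion interval in exclusion 8 runs back from C1D1 and not from the undated blood count that decides exclusion 7, so a transfusion-supported count can qualify a patient

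*Combined protocol and SAP*

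**What the plan says.** - **Count limits.** Exclusion 7 (section 4.3), "Impaired hematopoietic function with either", lists minimum white cell, neutrophil, hemoglobin and platelet values. It gives no date for the sample and does not ask for an unsupported count.
- **Transfusion interval.** Exclusion 8 excludes "Blood (or blood product) transfusions or blood growth factors within 7 days of C1D1".
- **Sub-item 8a.** Directly below, growth-factor support is called acceptable, with erythropoietin, darbepoetin, G-CSF, GM-CSF and platelet stimulators named. Patients must also have been free of platelet transfusion for more than a week in order to enrol.
- **When eligibility is checked.** "Inclusion and exclusion criteria" is listed in section 6.1.1, "Screening Visit (-21 to -1 days before start of treatment"), and marked only at Screening in Table 2. It is not in the C1D1 list (section 6.1.2.1).
- **C1D1.** Section 6.1.2.1 schedules "CBC with differential" and attaches no limit or action to the result. Section 7.8.13 (day-one dosing) requires negative pregnancy tests where applicable and refers to renal and hepatic impairment. It contains no blood-count condition.
- **Later cycles.** Section 7.8.14, headed for a subsequent cycle, sets ANC and platelet conditions under the words "A new course of treatment may begin on the scheduled day 1 of a new cycle if".
- **Withdrawal.** Section 8.2 lets the investigator withdraw a participant who meets an exclusion criterion, including one newly developed. Those who consent "and receive the study intervention, and subsequently withdraw, or are withdrawn or discontinued from the study, will not be replaced".

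**The concern.** Two criteria that seem meant to work together are tied to different dates. The interval without transfusion is fixed to the first dose, while the count may be up to three weeks older. A patient can be transfused, sampled soon afterwards, found eligible on the supported value, and then wait out the 7 days before C1D1. By then the unsupported count may be below the entry limit, and the plan does not say that anyone must act on it.

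What is at stake is who is dosed. Section 7.7.1.1 names thrombocytopenia and neutropenia as potential overlapping toxicities of selinexor with pomalidomide, so the count at the first dose matters. Once dosed, a patient cannot be replaced and stays in the analysis population (sections 8.2 and 12.1). With two enrolling sites, an unwritten habit of checking the C1D1 result may not be applied in the same way at both.

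**Working it through.** The plan states no figure on this point, so there is none to reproduce. The check enumerates what the timing rules allow.

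**Inputs**
- Screening count taken c whole days before C1D1, with c = 1 to 21 (section 6.1.1).
- Transfusion given t whole days before C1D1.
- Exclusion 8 taken as passed when t > 7, so a transfusion exactly 7 days before C1D1 is treated as barred.
- For this check, a count is called transfusion-supported if taken 0 to 7 days after the transfusion, that is 0 ≤ t − c ≤ 7. The 7 days are borrowed from exclusion 8; the plan defines no such term.

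**1. One example.** Red cells on day -9 (t = 9), CBC on day -8 (c = 8). Exclusion 8: 9 > 7, passed. The count was taken 9 − 8 = 1 day after transfusion, and exclusion 7 accepts it.

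**2. All combinations as written.** Each of the 21 values of c has 8 values of t (c to c + 7): 21 × 8 = 168 pairs. A pair fails exclusion 8 only if t ≤ 7, which requires c ≤ 7. There are 7 such pairs for c = 1, 6 for c = 2, and so on down to 1 for c = 7: 7 + 6 + 5 + 4 + 3 + 2 + 1 = 28. So 168 − 28 = 140 pairs pass. Every screening day has at least one passing pair; even a CBC on day -1 can follow a transfusion on day -8 (8 > 7, and 8 − 1 = 7).

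**3. Interval counted from the qualifying CBC.** The condition becomes t − c > 7. All 168 pairs have t − c ≤ 7, so none passes.

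**4. C1D1 CBC as the qualifying count.** Here c = 0, and a supported count needs t ≤ 7. Exclusion 8 already bars t ≤ 7, so no pair passes. Either wording closes the gap.

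**5. Platelets under 8a.** More than a week must separate the last platelet transfusion from enrolment. In the example, 9 − 1 = 8 days, so the patient passes if enrolled on day -1 or later. With a transfusion on day -21 and a CBC on day -20, enrolment on day -13 (21 − 13 = 8 days) already suffices, and the qualifying count is still one day post-transfusion. 8a removes some paths and leaves others.

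**6. Is the C1D1 count checked elsewhere?** Exclusion 4 names its time point: toxicity "which has not resolved to at least Grade 2 or better by Cycle 1 Day 1 (C1D1"). Table 2, footnote 8, fixes the response laboratory tests to Day -1 or pre-dose C1D1. Exclusion 7 has neither. Section 7.8.13 has no count condition. Section 7.8.14 has ANC and platelet conditions, but for a subsequent cycle, and none for hemoglobin, the value most exposed to this route. Withdrawal under section 8.2 is at the investigator's discretion and is not a pre-dose check.

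**The case against.** The strongest reply is that 8a and ordinary care leave little of the gap.

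- **8a covers platelets and growth factors.** This stands in part. The platelet rule narrows the platelet route. Because 8a calls growth-factor support acceptable, the plan cannot be said to require unsupported counts throughout, and no section states that purpose. The growth-factor issue is instead that exclusion 8 and its own sub-item contradict each other. What is left of the gap is mainly red-cell transfusion and hemoglobin.
- **The C1D1 CBC will be seen.** Exclusion 7 is undated, so a site may apply it to that result, and someone who has consented but not been dosed may be replaced. Both are possible, but neither is required.
- **Section 7.8.14 speaks of a new course of treatment.** Its opening sentence could be stretched to Cycle 1, but its heading and its references to the previous cycle point to later cycles.
- **Low counts are manageable.** Table 4 handles Grade 2 or 3 thrombocytopenia without bleeding by dose reduction and consideration of platelet growth factors, and removal follows only a delay beyond 28 days or four weeks (sections 7.7.1 and 7.8.14). A reader might infer that such patients would leave early, count as non-responders and lower the ORR by a set amount. The documents do not show that.

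**Conclusion.** The gap is real but limited. As worded, exclusions 7 and 8 can both be met on a transfusion-supported count, chiefly hemoglobin after red cells and, less readily, platelets. The plan does not say whether the C1D1 count must still meet exclusion 7. The 140 of 168 combinations describe what the wording permits under the day conventions above; they are not a probability.

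Three further inferences are not supported.
- **A share of patients.** A reader might note that days -21 to -8 are 14 of the 21 screening days and take that as the exposure. It covers only a CBC on the day of transfusion, and it is a share of calendar days. The documents do not say how many patients are transfused during screening.
- **A link to deaths.** Section 2.4.1.4 reports fatal events with selinexor, pomalidomide and dexamethasone, but nothing ties them to counts at entry.
- **Shift-table baseline.** Whether baseline means Screening or C1D1 is unclear regardless of any transfusion, and the change proposed here would not settle it.

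The case for amending rests on clear wording, a direct bearing on who is dosed, and a very low cost.

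**What to change.** 1. In exclusion 8, count the 7-day transfusion interval back from the CBC used for exclusion 7 as well as from C1D1.
2. In exclusion 7, state which dated count decides eligibility. The CBC already scheduled for C1D1 could serve; the result would then have to be read before dosing. The count limits stay as they are.
3. In the same edit, reconcile exclusion 8, which bars growth factors within 7 days, with 8a, which accepts them. Which of the two governs is for the sponsor to decide.
4. The sponsor should reconcile the absence of a count condition in section 7.8.13 with the conditions in section 7.8.14, and say what status the C1D1 count has.

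The cost is a few sentences and no new test. Some starts may be delayed and a few patients may fail screening, but section 4.5 already allows rescreening for impaired hematopoietic function. The patient transfused on day -9 could still qualify within the window on a CBC drawn on day -1, since 9 − 1 = 8 days is more than 7.

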#### **4.4 Lifestyle Considerations**

Not applicable.

#### **4.5 Screen Failures**

Screen failures are defined as participants who consent to participate in the clinical trial but are not subsequently assigned to the study intervention or entered in the study. A minimal set of screen failure information is required to ensure transparent reporting of screen failure participants, to meet the Consolidated Standards of Reporting Trials (CONSORT) publishing requirements and to respond to queries from regulatory authorities. Minimal information includes demography, screen failure details, eligibility criteria, and any serious adverse event.

Individuals who do not meet the criteria for participation in this trial (screen failure) because of impaired liver, renal or hematopoietic function may be rescreened. Rescreened participants should be assigned the same participant number as for the initial screening.

#### **4.6 Strategies for Recruitment and Retention**

Participants will be recruited by their primary oncologist at Weill Cornell Medicine and NewYork Presbyterian-Brooklyn Methodist Hospital. We estimate a study sample size of 26 participants without gender, race, ethnicity or age targets, and an anticipated accrual rate of 2 subjects per month.

Potential participants will be identified by their primary oncologist and approached by a co-investigator; the study coordinators will keep records of monthly screening and enrollment logs at each site. No other recruitment strategies are planned. Vulnerable participants are not eligible for this study. Participants will receive a \$50 stipend for each completed study visit at Weill Cornell Medicine and NewYork Presbyterian-Brooklyn Methodist Hospital. The stipend will be provided via Clincard.

### **5. Registration Procedures**

#### **5.1 Subject Registration (WCM only)**

Subjects will be registered within the WRG-CT as per the standard operating procedure for Subject Registration.

## 5.2 Subject Registration (Sub-sites)

Study participants will be centrally registered with the Weill Cornell Medicine Joint Clinical Trials Office (JCTO). To register a new study subject, email the following documents to [contact] :

- Completed WCM subject registration form
- First and last page of the fully executed informed consent form, plus additional pages if checkboxes for correlative studies are required
- Fully executed HIPAA research authorization form
- Eligibility checklist signed and dated by investigator and research nurse
- Documentation of any eligibility waivers granted
- Source documentation to verify eligibility

Note that attachments larger than 4.5 MB are not accepted, so larger attachments should be split into more than one email. Central registration information is reviewed and entered into the REDCap database.

## 6. Study Procedures

### 6.1 Schedule of Assessments

**Table 2. Schedule of Activities (SOA)**

Activity/ Assessment	Screening		C 1		C 2		C ≥ 3		EoT Visit		FU Assessment		DOR and Survival FU
	D-21 to D-1	D1	D8 ± 1d	D15 ± 1d	D1 ± 2d	D15 ± 2d	D1 ± 2d	D15 ± 2d	≤14d after LD	30d after LD ± 7d	every 3m after LD for 12m ± 14d		
Informed consent	X												
Medication dispensation (1)		X			X		X						
Patient History													
Inclusion and exclusion criteria	X												
Demographics	X												
Medical history (2)	X												
Adverse events	X	X	X	X	X	X	X	X	X	X			
Concomitant medications	X	X			X		X	X					
Dose intensity (3)		X			X		X	X					

QOL assessment (4)	X	X			X	X	X	X
Telephone contact (5)							X	X
Physical Examination								
Patient height	X							
Patient weight	X	X	X	X	X	X	X	
Vital signs (BP, pulse, temperature)	X	X	X	X	X	X	X	
Complete physical examination	X						X	
Symptom-directed physical examination		X	X	X	X	X	X	
12-lead ECG		X						
ECOG Performance Status	X			X		X	X	
Clinical Labs								
CBC with differential	X	X	X	X	X	X	X	
TSH		X						
Complete serum chemistry (6)	X	X	X	X	X	X	X	
Pregnancy test (7)	X	X			X		X	
Multiple Myeloma Disease Assessments								
SPEP and serum immunofixation (8)	X	X			X	X	X	X*
UPEP (24-hr urine) and urine immunofixation (8)	X	X*			X	X	X	X*
Quantitative Ig levels (8)	X	X			X	X	X	X*
Serum FLC (8)	X	X			X	X	X	X*
$\beta$ 2-microglobulin	X							
Skeletal survey (9)	X				X*	X*	X*	X*
Plasmacytoma assessment (10)	X	X*			X*	X*	X*	X*
Bone marrow biopsy and aspirate (11)	X				X*	X*	X*	

\* indicates that additional schedule information is provided in the footnotes. Merged cells indicate that the procedure may be performed during either Screening or the C1D1 visit.

Abbreviations: BP = blood pressure; BSA = body surface area; CBC = complete blood count; D = day; DOR = duration of response; ECG = electrocardiogram; ECOG = Eastern Cooperative Oncology Group; EoT = End of Treatment; FLC = free light chain; FU = follow-up; Ig = immunoglobulin; LD = last dose; M = month; MM = multiple myeloma; QOL = quality of life; SPEP = serum protein electrophoresis; UPEP = urine protein electrophoresis; Y = year.

Footnotes:

1. Only enough selinexor for 1 cycle will be provided to the patient at the beginning of each cycle.

2. Includes baseline symptoms as well as a detailed history of prior cancer therapies, especially MM therapies, including start and stop dates, disease progression during or after therapy, as well as discontinuations due to intolerance or any other serious illness. Collect data on cigarette smoking status and, if current smoker, counsel regarding smoking cessation per institutional guidelines.
3. Dose intensity assessments involve the use of subject medication diaries, provided on C1D1 and assessed on day 1 of every cycle beginning at cycle 2.
4. QOL assessment as measured by the Functional Assessment of Cancer Therapy - MM (FACT-MM). See Appendix 6.
5. Telephone call (or visit) for:
  - a. Follow-up assessment to evaluate adverse events.
  - b. Durability of Response and Survival Follow-up: After treatment discontinuation, if possible and feasible for patients whose disease is not progressing, a telephone call will be made to the patient (or the patient's family) every 3 months for 18 months to inquire about the patient's survival, MM status, and information on any antineoplastic therapies utilized since discontinuation of study treatment, as well as available SPEP with serum immunofixation, UPEP with urine immunofixation, serum FLC, quantitative Ig levels, and plasmacytoma assessment when clinically appropriate.
6. Complete serum chemistry must include serum potassium and magnesium levels.
7. For women of childbearing potential, a serum hCG pregnancy test must be performed during Screening and at EoT Visit. After an initial negative serum hCG pregnancy test during Screening, urine pregnancy tests may be performed instead of serum testing. Women of childbearing potential require two negative pregnancy tests prior to receiving the first dose of study treatment (at Screening and at C1D1).
8. Response criteria include SPEP, serum immunofixation, quantitative Ig levels, and serum FLC assay on C1D1 and measurements must be taken either on Day -1 or pre-dose on C1D1. These are in addition to the disease assessments performed during Screening for enrollment. UPEP (24-hr urine) and urine immunofixation may be omitted on C1D1 if performed adequately during screening within  $\leq$  7 days.
9. Skeletal survey to be performed using X-rays, MRI, CT or PET/CT per institutional guidelines. Bone lesions seen at Screening should be re-assessed during the study using the same imaging modality that was used at Screening. Repeat scans should be done at a clinically appropriate frequency, as determined by the Investigator.
10. If plasmacytomas are detected at baseline by physical examination, they should be re-assessed during the physical exam on D1 of each cycle and at the EoT visit.
11. Bone marrow samples:
  - a. At Screening, aspirate and biopsy for:
    - i. Morphology, flow cytometry and FISH analysis to confirm diagnosis and classification
    - ii. Clonotype identification for subsequent MRD analysis
  - b. At suspicion of CR (negative serum and urine immunofixation), aspirate and biopsy for:
    - i. Morphology, flow cytometry and FISH analysis to confirm CR and/or sCR
    - ii. Aspirate for MRD analysis
  - c. At suspicion of progressive disease, if clinically appropriate, aspirate and biopsy for:
    - i. Morphology, flow cytometry and FISH analysis to confirm progressive disease

